# **Qualitative Endpoints**

For qualitative interviews, we aim to interview people with a diversity of intervention fidelity, acceptability, usability, feasibility, and appropriateness. This is an exploratory interview study in nature, so idea generation and exploration are the goals (not thematic saturation). We aim to interview PLANTS (n=20-30) and EMAILS (n=10-20) participants, and these sample sizes will provide us with ample information about the CFIR domains.

#### 9.3 Populations for Analyses

We will analyze data from the following populations:

- PLANTS Primary Endpoint Population: This includes all participants who were in the PLANTS study arm and have AIM, IAM, or FIM data as reported in the follow-up survey.
- Intention-to-Treat (ITT) Analysis Population: This includes all staff participants who enroll in the study.
- Per-Protocol Analysis Population: This includes all staff participants who enroll in the study.
- PLANTS Condition Population: Staff participants in the PLANTS arm.
- EMAILS Condition Population: Staff participants in the PLANTS arm.
- Qualitative Interview Population: Staff who participate in interviews.

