#### 4.3 Justification for Intervention

We decided to deliver PLANTS using an online design because this model is more scalable than traditional inperson trainings, thereby reaching more people. We include both synchronous and asynchronous modules, as there is evidence that both is better than asynchronous training only. The length of the intervention evolved throughout the development of the project with feedback from the community. The number of asynchronous elements were identified through our intervention mapping process and by chunking PLANTS' performance objectives into complementary components. The lengths of videos were determined based on expertise provided by teaching and learning experts. Because this is a pilot study including intervention adherence, a participant will have to complete at least one item in the PLANTS intervention to have evaluable data.

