#### 5.5 Strategies for Recruitment and Retention

#### School Staff

**Recruitment.** For high schools to be eligible to enroll in our study, school administrators must be willing to provide email addresses for all school staff members so that we can adequately recruit all staff in the high school. At the enrolled high schools, we will administer online surveys via REDCap to all staff members that interact with students (e.g., a census of teachers, administrators, nurses, counselors). We will email participants a screener survey to confirm their eligibility for participation, a consent form, and a baseline survey. We will also place study advertisements in their school mailboxes.

**Retention.** The follow-up survey will be delivered post-intervention. Several methods used by [name] and his mentorship team have proven valuable in retention of participants in longitudinal studies. To keep participants engaged, we will: inform participants at the beginning about the anticipated time burden and associated incentives; provide participants with clear instructions about their tasks; send personalized reminder emails and text messages to participants who have not completed a survey; email participants 1 day in advance of their survey, reminding them to look out for the upcoming survey email and to check spam filters; encourage participants to reach out to us when they have questions or concerns via email, phone, or text; and provide participants with escalating incentives that increase each survey. We will monitor retention on a weekly basis and more frequently if needed to ensure we are maintaining high retention.

**Incentives.** To incentivize school staff to complete the baseline survey, we will provide \$20 gift cards to each participant and will raffle \$30 gift cards to 20% of participants who take the baseline survey within each school. To incentivize school staff to complete the follow-up survey, we will provide \$30 gift cards to each participant who completes the survey will and raffle \$40 gift cards to 20% of participants who take the follow-up survey within each school. For staff who complete the follow-up interview, we will provide \$50 incentive as a thank you for their time.

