#### Primary Endpoint Hypothesis:

We hypothesize that high school staff will rate the PLANTS intervention as having high acceptability, usability, appropriateness, and feasibility in the follow-up survey. We based our benchmarks of success (which are means >3.75 out of 5 for FIM, AIM, IAM and > 70 out of 100 for SUS) on prior research.

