#### 9.2 Sample Size Determination

#### Primary Endpoints

To adequately evaluate the primary endpoints, we need precise estimates of acceptability, appropriateness, and feasibility. We calculated our sample size based on our primary outcomes, a 5% error rate, and best practices for feasibility studies. The median number of teachers at each MetroWest Region high school is n=86. With 4 schools in our sample, we anticipate inviting a total  $\geq$ 344 school staff to participate in the pilot study. Assuming 50% agree to participate, 50% of participants are in the PLANTS study arm, and 75% of PLANTS participants complete the follow-up survey (reduced n=65), we can estimate 95% CI widths  $\leq$ 0.33 for AIM, IAM, and (based on the largest upper CI limit of the AIM, IAM, and FIM standard deviations) and  $\leq$ 10.1 for SUS. Such precision levels are sufficient.

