#### 9.4.2 Analysis of the Primary Endpoints

To answer our primary research question, we use best practices for pilot/feasibility studies. Thus, we will analyze our primary outcomes using descriptive statistics. We will not correct for multiple tests. AIM, IAM, and FIM are calculated as an average of their 4 respective items in the follow-up survey. We will calculate SUS as recommended. Among people in the PLANTS primary endpoint population, we will calculate means and 95% CIs for participants' responses to the FIM, AIM, IAM, and SUS. Our benchmarks of success are means > 3.75 out of 5 for AIM, IAM, FIM and scores > 75 out of 100 for SUS.

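### Section 4.3 requires one completed PLANTS item for evaluable data, but the Section 9.3 primary population has no exposure condition, so the primary means can include ratings from staff who never used the course

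*Combined protocol and SAP*

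**What the plan says.** Two places in the combined protocol and SAP say whose course ratings count.

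- Section 4.3 (Justification for Intervention) sets a minimum exposure: "a participant will have to complete at least one item in the PLANTS intervention to have evaluable data".
- Section 9.3 (Populations for Analyses) defines the PLANTS primary endpoint population by arm and by available scale data: "This includes all participants who were in the PLANTS study arm and have AIM, IAM, or FIM data as reported in the follow-up survey". It neither states nor cites the one-item rule, and SUS is not among the qualifying scales.

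Section 9.4.2 then says that, in this population, "we will calculate means and 95% CIs for participants' responses to the FIM, AIM, IAM, and SUS". SUS is therefore analysed in a set defined by the other three scales, although Section 8.1 names usability as the fourth primary outcome.

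The primary objective is judged by point estimates against thresholds: "Our benchmarks of success are means > 3.75 out of 5 for AIM, IAM, FIM and scores > 75 out of 100 for SUS". Section 9.1 gives a different SUS threshold, "> 70 out of 100 for SUS".

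**The concern.** The one-item rule and the Section 9.3 definition select different people whenever a PLANTS-arm participant answers the scales without having completed an item. Several features of the plan leave room for this:

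- Section 4.4 defines study completion by the baseline and follow-up surveys alone.
- Section 5.5 pays the follow-up incentive as "gift cards to each participant who completes the survey", with no course-use condition.
- Section 7.3 pursues survey non-responders by phone, text and email, whatever their course use.
- Section 8.1 gives the scales to staff participants at follow-up without stating an exposure screen.

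The sample items in Section 8.1 are worded in the past tense about the course, for example whether it was easy to use. An answer from someone who never opened it does not describe experience of using it.

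The primary result is four means set against thresholds, so who counts in the mean can decide the result. With two rules in the document, the choice could also be made after the ratings are seen.

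**Working it through.** **1. The planned n.** Section 9.2 gives 344 invited staff, 50% participation, 50% in the PLANTS arm and 75% completing follow-up.

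n = 344 × 0.50 × 0.50 × 0.75 = 64.5, rounded up to 65.

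This reproduces the stated 65. No factor allows for non-exposure, so the figure matches Section 9.3 and not Section 4.3.

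**2. Tipping point for the 5-point scales (illustration).** The documents give neither a share of never-starters nor any ratings, so the inputs here are assumptions. With user mean U, never-starter mean V and k never-starters among 65 responders, the Section 9.3 mean is U − (U − V) × k/65. Under the one-item rule it stays at U. The table takes V = 3.0, the scale midpoint.

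| U | Smallest k giving a mean at or below 3.75 | Resulting mean |
|---|---|---|
| 3.8 | 5 (8%) | 3.8 − 0.8 × 5/65 = 3.738 |
| 3.9 | 11 (17%) | 3.9 − 0.9 × 11/65 = 3.748 |
| 4.0 | 17 (26%) | 4.0 − 1.0 × 17/65 = 3.738 |
| 4.2 | 25 (38%) | 4.2 − 1.2 × 25/65 = 3.738 |

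**3. Tipping point for SUS (illustration).** Assume users average 78 and never-starters 50.

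- Seven never-starters give 78 − 28 × 7/65 = 74.98, below the Section 9.4.2 threshold of 75.
- Nineteen give 78 − 28 × 19/65 = 69.8, below the Section 9.1 threshold of 70.

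**4. Precision if the one-item rule is applied.** Section 9.2 states 95% CI widths of at most 0.33 (5-point scales) and 10.1 (SUS) at n = 65. The SDs come from cited sources and are not in the documents, so the widths cannot be checked directly. Solving width = 2 × 1.96 × SD/√65 gives SD of about 0.68 and 20.8. Reading width as full width agrees with the proportions in Section 9.2: 2 × 1.96 × √(0.25/n) gives 0.106, 0.149 and 0.211 at n = 344, 172 and 86, against the stated 0.11, 0.15 and 0.21.

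Holding the SD fixed, the width at n = m is the stated width × √(65/m):

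| Assumed never-exposed among 65 | m | AIM/IAM/FIM width | SUS width |
|---|---|---|---|
| 3 (about 5%) | 62 | 0.34 | 10.3 |
| 6 (about 10%) | 59 | 0.35 | 10.6 |
| 13 (20%) | 52 | 0.37 | 11.3 |
| 20 (about 30%) | 45 | 0.40 | 12.1 |

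**5. The SUS omission.** Read literally, a PLANTS participant with SUS data but no AIM, IAM or FIM data falls outside the population and is lost from the SUS mean. A member with no SUS score contributes nothing to that mean. This is separate from step 2, because omitting SUS does not admit unexposed raters.

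**The case against.** The strongest reply is that the two sections are cumulative: Section 4.3 says what makes data evaluable, Section 9.3 says which arm and scales define the set, and only a cross-reference is missing. That reading is possible. It still leaves Section 9.3 describing all PLANTS-arm participants with scale data, and Section 9.2 with an n and interval widths that ignore the exposure rule. The text needs changing on either reading.

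Other parts of the defence stand:

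- **Presence of never-starters.** A reader might infer that they will certainly be in the data. The documents do not support that. Section 9.3 admits only responders with AIM, IAM or FIM data, Section 2.3.3 lets participants skip questions, and Section 6.4 says those who have not completed modules or events will be contacted. Section 8.1 neither states nor rules out survey branching.
- **Validity of their ratings.** A reader might infer that every rating from a non-user is meaningless. Section 8.1 frames most of these outcomes as perceptions, and perceived relevance does not plainly require use. Not opening the course may itself reflect low acceptability. Keeping all responders is therefore a defensible choice, and conditioning on uptake could flatter the course.
- **Size.** The ratings in the illustration are assumed, with user means set not far above the thresholds. Never-starters could also rate high.
- **Visibility of uptake.** Adherence is reported separately under Section 9.4.3, so low use would not vanish from the report.

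A reader might also take the one-item rule to remove PLANTS never-starters from the efficacy comparison. Section 9.3 defines ITT as all enrolled staff and Section 9.4.3 bases efficacy primarily on it, so that reading is strained. One sentence would rule it out.

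**Conclusion.** The point holds in this form: the stated exposure rule and the stated primary population do not match, and the planned n follows the population without the rule. The four primary means can include ratings from staff who never used the course, and the choice between the two sets could change whether a benchmark is met.

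How likely that is cannot be determined from the documents. On the assumed midpoint ratings it takes between 5 and 25 of 65 responders, depending on how far the users' mean lies above 3.75. The direction of any shift is not fixed, so a finding that the planned means are biased downwards would go too far.

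The SUS omission is real but minor, since it matters only for someone who leaves the other three scales blank and still completes SUS.

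This should be fixed before the data are analysed. In a pilot with a descriptive primary analysis and separate reporting of uptake, it does not undermine the design.

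**What to change.** Put one prespecified rule in both sections:

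1. Apply the protocol's own one-item rule to the four rating endpoints, and state whether attending a Live Zoom Event counts as an item. Section 9.4.3 counts module items and events separately, so this is a decision to record and should not be assumed.
2. Analyse each of AIM, IAM, FIM and SUS in those who have that score.
3. Beside each mean, report the number of never-starters among responders and the all-responder mean, so that low uptake is not hidden.
4. State that the rule does not apply to the ITT efficacy or safety analyses.
5. Restate the expected n and CI widths in Section 9.2 under an explicit assumption about non-exposure.

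The SUS thresholds in Sections 9.1 and 9.4.2 should be reconciled at the same time, since the population question cannot be judged against two cut-offs.

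The cost is wording plus one extra result per scale. Section 6.4 already tracks Canvas completion and event attendance, so no new data are needed. The price is precision: for an assumed 5% to 30% never exposed, n falls to about 62 to 45 and the AIM/IAM/FIM width rises to about 0.34 to 0.40, against the stated 0.33.

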#### 6.4 Study Intervention Adherence

We will make the following efforts to confirm that the subject of the PLANTS intervention is adherent:

- Participants will be required to click "completed" in Canvas modules when they are completed.
- We will ask participants to register for the Live Zoom Events.
- We will track attendance at Live Zoom Events.
- We will contact participants if they have yet to complete the modules or Live Zoom Events.

Canvas module completion and Live Zoom Event attendance will be used to calculate study intervention adherence.

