### Additional Analyses

Participant bias assessment will compare staff participants' demographics (at baseline) to publicly available school-level data. We will report significant differences as potential validity threats.

Attrition bias assessment will compare staff respondents who completed follow-up surveys versus those who did not by baseline demographics and outcomes.

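### The primary benchmarks are judged on follow-up responders only, with 25% loss planned and nothing that shows whether a pass would survive non-response

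*Combined protocol and SAP*

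**What the plan says.** Section 9.3 defines the primary endpoint population as PLANTS-arm participants who "have AIM, IAM, or FIM data as reported in the follow-up survey". Section 9.4.2 states that "we will analyze our primary outcomes using descriptive statistics", and specifies: "Among people in the PLANTS primary endpoint population, we will calculate means and 95% CIs" for FIM, AIM, IAM and SUS. The benchmarks there are "means > 3.75 out of 5 for AIM, IAM, FIM and scores > 75 out of 100 for SUS". Section 9.1 gives the same 3.75 for the three implementation scales but a SUS benchmark of 70.

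The sample size in Section 9.2 assumes that "75% of PLANTS participants complete the follow-up survey", which leaves 65 people.

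Other parts of the plan touch on non-response:

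- Sections 4.1 and 6.3 name attrition bias as a risk of the unblinded design.
- Section 9.4.3 reports attrition over all consented staff, and adherence among PLANTS participants, as separate endpoints.
- Under Additional Analyses, Section 9.4.3 adds: "Attrition bias assessment will compare staff respondents who completed follow-up surveys versus those who did not", on baseline demographics and outcomes.
- Section 6.4 says that "Canvas module completion and Live Zoom Event attendance will be used to calculate study intervention adherence".
- Section 4.3 requires one completed course item before a participant's data count as evaluable. Section 9.3 does not repeat this condition.

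No weighting, imputation, bounding or tipping-point analysis is stated for the primary endpoints.

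**The concern.** The trial's primary conclusion is a pass or fail on four means, and Section 2.1 says the results will inform a fully powered trial. Each mean describes only the people who returned the survey. Staff who did not like the course, or who drifted away from it, may be less inclined to return a survey about it. If so, the means describe a more favourable group than the staff who were enrolled.

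The planned attrition comparison does not settle this. Neither Section 1.3 nor Section 8.1 places AIM, IAM, FIM or SUS at baseline. If the comparison means baseline outcomes, it contains no primary outcome; if it means follow-up outcomes, the non-completers have none. Either way, it does not feed into the estimate. The attrition and adherence endpoints disclose loss and disengagement, but they do not tell the reader whether a mean just above its benchmark would stay above it for the whole arm. The 95% CI covers sampling error among responders and nothing else.

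**Working it through.** **Reproducing the plan's n (Section 9.2).** Four schools at a median of 86 give 344 invited. 344 × 0.50 consent × 0.50 in PLANTS × 0.75 completing = 64.5, which rounds to the stated 65. The arm has 344 × 0.50 × 0.50 = 86, so about 86 − 65 = 21 people have no primary data.

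**Formulas.** Let R be the responder mean, N the mean the non-responders would have given, m the fraction missing and B the benchmark.

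- Whole-arm mean: M = (1 − m)R + mN
- Overstatement: R − M = m(R − N)
- Tipping point: N* = (B − (1 − m)R)/m. The benchmark must be exceeded, so it is missed when N is at or below N*.

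The documents give no value for N. What follows are tipping points and assumed ranges, not estimates.

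**Overstatement at m = 0.25.** Gaps of 0.25, 0.5 and 1.0 scale points give about 0.06, 0.125 and 0.25. SUS gaps of 5, 10 and 20 points give 1.25, 2.5 and 5.0.

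**Tipping points at m = 0.25.**

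| Scale and benchmark | R | N* | Shortfall R − N* |
|---|---|---|---|
| AIM/IAM/FIM, 3.75 | 3.8 | (3.75 − 2.85)/0.25 = 3.6 | 0.2 |
| | 3.9 | (3.75 − 2.925)/0.25 = 3.3 | 0.6 |
| | 4.0 | (3.75 − 3.0)/0.25 = 3.0 | 1.0 |
| | 4.25 | (3.75 − 3.1875)/0.25 = 2.25 | 2.0 |
| SUS, 75 (Section 9.4.2) | 80 | (75 − 60)/0.25 = 60 | 20 |
| SUS, 70 (Section 9.1) | 80 | (70 − 60)/0.25 = 40 | 40 |

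**Comparison with the planned precision.** Section 9.2 gives a CI width of at most 0.33 for the implementation scales, a half-width of 0.165. The gap that produces an overstatement that large is 0.165/0.25 = 0.66 points. The documents give no SD. Back-solving from the width gives 0.33 × √65/(2 × 1.96) ≈ 0.68, so 0.66 is about one implied SD. A responder mean of 3.75 + 0.165 = 3.915, whose lower limit just reaches the benchmark, would be brought down to 3.75 by that gap.

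**Sensitivity to the loss rate.** For R = 4.0, N* is 2.33 at 15% missing, 3.0 at 25%, 3.29 at 35% and 3.50 at 50%. The extreme bounds for R = 4.0 at 25% missing are 0.75 × 4.0 + 0.25 × 1 = 3.25 and 0.75 × 4.0 + 0.25 × 5 = 4.25.

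**The case against.** The strongest reply is that this is a pilot with a descriptive primary analysis, and that loss and disengagement are already visible. Attrition and adherence have their own benchmarks, course-embedded feedback is summarised (Section 8.1), and interviews aim for participants with varied fidelity and ratings (Section 9.2). Section 7.3 requires repeated contact attempts before loss is declared, and the gift card in Section 5.5 is paid for the survey, not for the course. A loss of 25% is also the most that the plan's own attrition hypothesis allows, not a known rate. All of this stands as disclosure and as effort to limit loss. None of it shows whether a benchmark verdict would hold for the whole arm.

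Two stronger readings are tempting, and the documents support neither:

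- A reader might infer that disengaged staff are removed and that the means are therefore biased upward. Section 9.3 sets no engagement condition, so staff who abandon the course but answer the survey are counted, subject to the one-item rule in Section 4.3. Nothing is known about non-responders' ratings, and the bias is zero if response is unrelated to rating.
- A reader might infer that the best predictor of response and satisfaction is collected and left unused. No passage shows that completion or attendance predicts either, and Section 9.4.3 uses both for the adherence endpoint. They are unused only in the primary means.

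The objection to weighting also has force. It cannot repair non-response driven by dislike that remains after completion and attendance are taken into account, it cannot supply a meaningful rating from someone who opened nothing, and it will be imprecise with about 65 responders. That is why the tipping-point table should come first.

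**Conclusion.** The concern holds as a gap in the primary analysis. The plan judges its four benchmarks on unadjusted responder means, expects a quarter of the arm to be missing, and gives no means of telling whether the conclusion depends on who answered. Upward bias is plausible but not demonstrated.

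The size depends on how close the result is to the benchmark. Near 3.75 a small difference between responders and non-responders reverses the verdict; at 4.0 it takes a full point; at 4.25 reversal is unlikely, and the added analysis would then strengthen the claim. These figures rest on 25% missing and on assumed non-responder means. For SUS, the margin cannot be stated until the benchmarks of 70 and 75 are reconciled. This should be addressed before the data are seen, but it does not invalidate the design.

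**What to change.** Keep the responder mean and its 95% CI as the headline, and add the following to Section 9.4.2:

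1. Beside each mean, the number and fraction of PLANTS enrollees who contributed to it.
2. A pre-specified tipping-point table giving, for each scale, the non-responder mean at which the benchmark would be missed at the observed loss rate.
3. As a supportive analysis, a mean weighted or imputed on module completion, event attendance and baseline variables. State the target group as PLANTS enrollees who completed at least one course item, which also reconciles Sections 4.3 and 9.3. State too that the method assumes response is unrelated to rating given those variables.
4. One SUS benchmark, used in both Section 9.1 and Section 9.4.2.

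The cost is a little more analysis work and no new data collection. The supportive estimate will be imprecise at about n = 65, and the supportive means may be slightly lower than the headline ones.

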# 6.1.2 Administration and Dosing

PLANTS online modules will be administered online via Canvas. Sections will be opened once per month, and there are a total of 3 sections over 3 months. The synchronous Live Events will be administered via Zoom. There are a total of 3 events. A "Full Dose" of the PLANTS intervention includes completion of all the online modules and 3 Live Zoom Events. The Live Zoom Events are required to be administered by trained interventionists (the PI or Research Assistants). In the Live Zoom Events, participants will interact with each other and a shared interventionist in a virtual environment. Active control materials cannot be tracked as easily

because these online trainings are administered via other agency's websites (not the study team's website). There are no interventionists in the active control arm.

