#### Secondary Endpoint Hypotheses:

Regarding trial implementation and PLANTS safety, we hypothesize: school staff will have high participation rates in the study ( $\geq$ 50% consent); school staff will have a low attrition rate for the follow-up survey ( $\leq$ 25% drop-out); high school staff in the PLANTS arm will have high intervention demand ( $\geq$ 75% adhere to the intervention protocol); and high school staff in the PLANTS arm will have low adverse event prevalence ( $\leq$ 20% of PLANTS participants will report adverse events).

We hypothesize that participants in PLANTS will report greater active-empathic listening, greater self-efficacy for supporting, affirming, and protecting SGMY, and greater positive bystander intervention behaviors for bullying in follow-up surveys than participants in the active control arm.

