# Hypothesis: High school staff in the PLANTS arm will have high intervention demand (≥75% of enrolled participants will adhere to the PLANTS intervention).

Intervention Demand will be a variable ranging from 0-100%. Investigators assess PLANTS adherence, which is a composite variable ranging from 0% to 100%, comprised of 55% for module completion (based on the number of completed items divided by the total number of items offered) and 45% for Live Zoom Event attendance (where each event is 15%). These proportions are based on approximate time allocations.

Adherence is reflected by a score of 100%. We will calculate an overall adherence rate among PLANTS participants with a 95% confidence interval.

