# PLANTS Pilot Trial Version 1.0 Protocol STUDY21080178 2024.04.05 Hypothesis: High school staff participants in the PLANTS arm will report pre-post improvements in active- empathic listening, self-efficacy for supporting, affirming, and protecting sexual and gender minority youths, and positive bystander intervention behaviors for bullying.

To examine the pre-post changes in high school staff outcomes, investigators will first use descriptive statistics, such as means and percentages at each timepoint within arms. To test for within-arm statistical significance, investigators will use linear mixed models for continuous outcomes and generalized linear mixed models for binary outcomes, which account for within-school and within-person clustering using random effects. Investigators will estimate the intraclass correlations for within-school and within-person effects. These models will adjust for school size (*a priori* design variable).

Hypothesis: Participants in PLANTS will report greater active-empathic listening, greater self-efficacy for supporting, affirming, and protecting SGMY, and greater positive bystander intervention behaviors for bullying in follow-up surveys than participants in the active control arm.

We will use linear mixed models for continuous outcomes and generalized linear mixed models for binary outcomes—which account for within-school and within-person clustering effects (using random effects). We will estimate the intraclass correlations for within-school and within-person effects. Regression models will include a fixed term for school size (a priori design variable), intervention group (intervention or control), time (baseline or follow-up), and the interaction of intervention group × time (our variable of interest). The test of intervention effects on secondary outcomes will be primarily based on intent-to-treat estimates. We will estimate perprotocol effects in secondary models. If there are differences in potential confounders by intervention group, we will adjust for them in secondary multivariable analyses.

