# 9.4.7 Sub-Group Analyses

Primary endpoints will be analyzed based on gender, sexual identity, race/ethnicity, intrinsic religiosity, religious attendance, religious activity, and role in school. Average score differences will be estimated using mixed models with demographic characteristics as predictors and the primary endpoints as outcomes, adjusting for school clustering.

Secondary endpoints of PLANTS efficacy will be analyzed based on gender, sexual identity, race/ethnicity, intrinsic religiosity, religious attendance, religious activity, and role in school (i.e., effect modifiers). Multivariable models will contain the 3-way interaction term, all 2-way interaction terms, main effects of time, study arm, the potential effect modifier, and any variables that meaningfully differ between study arms at baseline. We will conduct both intent-to-treat and per-protocol analyses. A significant 3-way interaction suggests the presence of intervention effect heterogeneity. Following the approach of Kraemer to focus on effect size derivation, we will use Stata's postestimation "margins" command to probe the 3-way interaction terms to provide simpler meaningful results.

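### Section 9.3 defines the Per-Protocol population in the same words as ITT, so the per-protocol analyses in 9.4.3 and 9.4.7 would, with the same model, repeat ITT

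*Combined protocol and SAP*

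**What the plan says.** Section 9.3 lists six analysis populations. The second is "Intention-to-Treat (ITT) Analysis Population: This includes all staff participants who enroll in the study". The third is "Per-Protocol Analysis Population: This includes all staff participants who enroll in the study". Only the label differs.

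The per-protocol label is then used twice. For the between-arm comparison of staff outcomes, 9.4.3 says "The test of intervention effects on secondary outcomes will be primarily based on intent-to-treat estimates" and adds "We will estimate perprotocol effects in secondary models". For the seven effect modifiers, 9.4.7 says "We will conduct both intent-to-treat and per-protocol analyses". Neither place gives an inclusion rule or a different model.

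Text on adherence appears elsewhere:

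- **PLANTS, score.** In 9.4.3, Intervention Demand is a composite of 55% for modules and 15% for each of three live events. The section states "Adherence is reflected by a score of 100" (per cent). Section 6.1.2 describes the full dose in matching terms: "of the PLANTS intervention includes completion of all the online modules and 3 Live Zoom Events". Section 9.1 sets a target of at least "75% adhere to the intervention protocol".
- **PLANTS, one item.** Section 4.3, in a sentence that refers to intervention adherence, makes completion of at least one PLANTS item the condition for evaluable data.
- **PLANTS, number of events.** Section 4.1 gives two to three live events; 6.1.1, 6.1.2 and 9.4.3 use three.
- **EMAILS.** Link clicks are tracked (6.1.1, 6.2.1) and completion is self-reported (6.4). Section 6.1.2 concedes that the control materials are harder to track. No threshold is stated.

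**The concern.** A per-protocol analysis is meant to show the effect among staff who took part as intended. It needs either a set narrower than ITT or an estimator that uses adherence. The plan supplies neither, so anyone who follows 9.3 to the letter and keeps the 9.4.3 model will report the ITT result a second time under another name.

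The practical risk lies in how the gap gets filled. The trial is unblinded, and both 4.1 and 6.3 name biased intervention participation as a possible consequence. If the rule is written after adherence and outcomes are known, it can be chosen with the results in view. The open choices are real ones: which PLANTS rule applies, what cut-off on the score is used, and what counts as adherent in EMAILS. With four efficacy endpoints in section 3 and seven modifiers in 9.4.7, at least 4 × 7 = 28 per-protocol interaction analyses would inherit that choice, and 9.4.1 plans no multiplicity correction.

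**Working it through.** **1. Planned numbers (9.2).** Median 86 teachers per school × 4 schools = 344 invited. 344 × 0.50 = 172 enrolled. 172 × 0.50 = 86 in PLANTS. These match the plan. As a check on the denominators, the full width of a 95% interval for a proportion, 2 × 1.96 × √(0.25/n), is 0.106, 0.149 and 0.211 for n = 344, 172 and 86. The plan states 0.11, 0.15 and 0.21, which agree after rounding.

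**2. ITT against Per-Protocol as written.** Both sets are all enrolled staff: 172 − 172 = 0 excluded. The same model on the same rows gives the same estimate and standard error by construction.

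**3. Candidate PLANTS rules.**

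| Source | Condition | Linked to the Per-Protocol set? |
|---|---|---|
| 4.3 | at least one item completed | No; stated as the condition for evaluable data |
| 9.4.3 and 6.1.2 | score of 100%, or full dose | No; the score defines Intervention Demand |

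The two lie far apart: one admits a participant who finished a single item, the other only a participant who finished everything.

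**4. Does the 100% score hold together?** With three events, 55% + 3 × 15% = 100%, which agrees with 6.1.2. If only two were held, as 4.1 allows, the maximum would be 55% + 2 × 15% = 85% and nobody could reach 100%. If three are held and a participant completes every module but attends two, the score is also 85%: outside the set at 100%, inside it at any cut-off of 85% or lower.

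**5. How much a rule could matter (illustration only).** Assume three events and a 100% score as the PLANTS rule. The adherence rates below are assumptions, except that 75% is the plan's own target.

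| Adherent share | PLANTS staff kept | PLANTS staff excluded |
|---|---|---|
| 100% | 86 | 0 |
| 75% | 65 (0.75 × 86 = 64.5, so at least 65) | 21 (21/86 = 24.4%) |
| 50% | 43 | 43 |

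The 65 here counts adherent staff. The 65 in 9.2 counts PLANTS staff expected to complete the follow-up survey and is a different quantity. Under the one-item rule the number excluded would be those who completed nothing, which the documents do not let us estimate. For EMAILS no count can be derived.

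**6. Other entries in 9.3.** The PLANTS Primary Endpoint Population requires data on AIM, IAM or FIM, yet 9.4.2 analyses SUS in that same set. The omission affects only a respondent with SUS data and none of the other three scales. The EMAILS Condition Population is worded as the PLANTS arm; no analysis in 9.4 cites it by name.

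**The case against.** The best reply is that this is a copying slip with an obvious cure. The same list puts the EMAILS set in the wrong arm, no analyst would knowingly report one model twice, and the plan already holds adherence definitions that could serve. Per-protocol results are supportive only in a four-school pilot. A Manual of Procedures exists and was not available; it may contain the rule.

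Much of this stands. The duplicate sentence probably is a slip, and the consequence is limited. It would also be wrong to say that the documents offer no possible rule, since 4.3 and 9.4.3 each supply a candidate for PLANTS. But the cure is not obvious. The two candidates differ widely, neither is attached to this set, the 100% score conflicts with the number of events in 4.1, and EMAILS has no threshold at all. Nor can the deviation log settle the matter, because 9.5.10 treats nonadherence as an expected deviation that will not be reported. That section sends further detail on deviations to the Manual, but nothing says that the Manual defines the Per-Protocol set. A rule there would in any case leave a wrong definition standing in what 9.1 calls the formal analysis plan.

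**Conclusion.** The definition in 9.3 is wrong as it stands and should be corrected. Read literally and with the same model, the Per-Protocol set excludes 0 of the planned 172 staff and its results duplicate ITT. The condition matters: an adherence-adjusted estimator on all enrolled staff would give a different result, but none is described.

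Three stronger readings are tempting and not supported:

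- *That the trial's main conclusions are affected.* ITT leads the efficacy tests, the primary endpoints have their own set, and no benchmark in 9.1 or 9.4.2 rests on a per-protocol result.
- *That the full-dose rule is plainly intended, so about a quarter of PLANTS staff would be dropped.* No section makes that link. The 21 and 43 exclusions are illustrations under assumed adherence and three events, and no change in any estimate has been shown.
- *That the adherence definition is settled.* It agrees between 6.1.2 and 9.4.3 but not with 4.1.

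The SUS omission probably touches very few people, because all four scales sit in the same follow-up survey. The EMAILS label is editorial.

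**What to change.** Before outcome data are seen, replace the Per-Protocol sentence in 9.3 with option 1 or 2, or take option 3:

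1. **A rule for both arms.** For PLANTS, state a cut-off on the 9.4.3 adherence score, after reconciling 4.1 with 6.1.2 and 9.4.3 on the number of live events, and say how the one-item condition in 4.3 relates to it. For EMAILS, state a threshold on tracked link clicks, self-reported completion, or both.
2. **All enrolled staff with a named adherence-adjusted estimator.**
3. **Deletion** of the per-protocol analyses from 9.4.3 and 9.4.7.

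Under 1 or 2, record as a limitation that adherence is measured differently by arm (Canvas completion and event attendance against clicks and self-report), and that a click shows opening, not completion. If clicks are used, settle which system sends the links, since 6.1.1 names REDCap and 6.2.1 names Qualtrics.

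In the same edit, add SUS to the data condition of the PLANTS Primary Endpoint Population and define the EMAILS Condition Population as staff in the EMAILS arm.

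The cost is low. Option 3 removes two sentences. Options 1 and 2 need one analytic decision and use adherence data that the protocol already plans to collect; the hardest part is a defensible EMAILS threshold, given the limited tracking.
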